The goal of the third phase of FFT certification process is to move into a partnering relationship between the provider and FFT-LLC to assure on-going model fidelity, as well as impacting issues of staff development, interagency linking, and program expansion.

For this efficacy study, the control condition will be the usual services that would available for the YP and their family delivered to YP in child social care and related agencies. Prior to recruitment and randomisation a potential SAU intervention will be identified and selected by the caseholding practitioner in a consultation with the FFT-G supervisor/supervisor-in-training. The nature of the intervention will vary depending on availability in each site and the particular needs of the YP but there will be existing services in the local authority that are available for cases with contextual risk. This will be decided by caseholders prior to randomisation to ensure that an SAU intervention is available directly after randomization. All YP and Primary Caregivers (PCG) will be reimbursed for each assessment with a £30 shopping voucher. The intervention will be delivered to RCT participants between June 2024 and March 2026, with 6 month boosters provided to some families between April and September 2026. Booster sessions are follow-up sessions intended to consolidate the family's learning and knowledge especially to help resolve or overcome setbacks and new challenges. A caseholder or family member can request boosters directly from the FFT-G service.

Figure 1: FFT-G logic model

Impact evaluation

Research questions or study objectives

1. What is the difference in the volume (or variety) of self-reported delinquency between YP randomised to receive FFT-G and those randomised to receive SAU?
2. What is the difference in secondary outcomes between YP randomised to receive FFT-G and those randomised to receive SAU?
3. ~~What mediates~~ Do any proposed mediators mediate the relationship between intervention arm and self-reported delinquency? Potential mediators include parental supervision and monitoring, family functioning, parental and YP self-efficacy and YP attachment representations.
4. ~~What moderates~~ Do any proposed moderators moderate the effect of treatment and are there subgroup differences? Specific moderators include callous-unemotional traits, temperamental irritability, presence of offending behaviours at baseline.

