	measure (instrument, scale, source)	
YP mental health and adjustment measured by Parent and YP report: Strengths and Difficulties Questionnaire (Goodman, 2005)
 
Child Criminal Exploitation measured by YP report: SRD4 additional items.
 
Substance Misuse measured by YP report: ISR3 substance misuse subscale.
 
Parental mental health measured by parent report: DASS-21 (Henry & Crawford, 2005)
 
Parenting supervision, knowledge and YP disclosure measured by YP report: ISR3.
 
Family Functioning measured by YP and parent report: SCORE-15 (Fay et al., 2013)
 
Parental self-efficacy measured by parent report: BPSES (Woolgar et al., 2023)
 
Attachment representation measured by YP report: AAQ (Bodfield et al., 2020)
 
YP self-efficacy measured by YP report: NGSE (Chen et al., 2001)
 
CU traits measured by YP and parent report: CU Traits MAP (Hawes et al., 2020)
 
Temperamental irritability measured by YP report: ODD subtyping DSM items (Stringaris & Goodman, 2009)

		
YP School attendance and truancy measured by parent report; and YP report from ISRD4
 
Age; gender; ethnicity; SES; household composition; parent relationship to YP measured by parent and/or YP report
 
Service being seen; days from first caseworker contact to randomisation measured by administrative data

--	--	---

Design

This will be a parallel, two-armed, multi-site, efficacy randomised controlled trial of FFT-G compared to Services as Usual (SAU) interventions, in child social work, youth offending and early intervention services for YP at risk of Child Criminal Exploitation (CCE). The YP will be the unit of randomisation with an allocation ratio of 1:1, stratified by recruiting site. All study participants will have an allocated caseworker and will receive statutory or other services provided or organized by child social care and other agencies (e.g., early help, Youth Offending Services). In addition, the intervention arm will receive FFT-G and the SAU arm will receive additional specialist services identified prior to recruitment by child social care and early help service managers or caseworkers in collaboration with Family Psychology Mutual (FPM), the grantee who will deliver FFT-G.

Randomisation

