- Index child/young person is actively homicidal, suicidal or psychotic.
- Problem sexual behaviour is the central concern.
- Presence of organic and/or cognitive conditions that may have prevented family members making use of talking therapy.
- Key family members, defined as “major players” in FFT-G, refuse family-based therapy.
- Significant child protection concerns: basic needs of children are not being met.
- Family have plans to move out of borough, thereby making therapy unfeasible within five months.

Screening for eligibility

- i) The embedded FFT-G supervisor/supervisor-in-training examines all new referrals to child social care and associated agencies for cases that meet eligibility criteria on the basis of reports produced from agency systems. These reports include all cases with the following categories of need: missing episodes (from home or care) reported to the Multi-Agency Safeguarding Hub (MASH), gang activity, criminal activity and sexual exploitation. If a case is identified as potentially eligible, it proceeds to consultation.
- ii) The FFT supervisor/supervisor-in-training attends internal meetings (e.g., with junior Family Intervention Team, Common Assessment Framework (CAF) coordinators and Youth Offending Service [YOS]) to discuss cases and proceeds to consultation (if potentially eligible).

Given that data on CCE, gang and CLDN involvement are not consistently recorded on case records, the aim of the screening conducted by the FFT-G team leader is primarily to identify if contextual risk **is** present.

Consultation

If a case is deemed potentially eligible, the FFT-G supervisor/supervisor-in-training will have a meeting or call with the practitioner who holds the case and determines eligibility after further discussion with the practitioner. They will also record if the referring practitioner believes that the YP is exhibiting offending behaviour. If the case is deemed eligible, an SAU service is identified (if it had not already been by the agency), should the case be randomised to SAU. SAU services in the FFT-G pilot included the following and we would expect these to be typical in this trial:

- Specialist exploitation social work interventions
- Parenting programmes
- One-on-one mentoring
- Activity-based community interventions
- Diversionary group-based work
- One-on-one counselling provisions (e.g. school-based, CAMHS, etc.)
- Gang-exit interventions

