Number of adults in the house (parent report)

Number of children/YP in the house (PCG report)

Service the YP was seeing (administrative data)

PCG relationship to YP (PCG report)

Number of days from first contact with a caseworker (typically consultation) and randomization (administrative data)

All collected at baseline only.

Compliance¹²

Data on treatment compliance is captured as routine clinical monitoring on the FFT CCS system and will be provide by FFT LLC (the developers) and FPM (the grantee delivering the FFT-G). This will include:

¹² Compliance here is equivalent to the broader term adherence.

Number of sessions received

Phases completed

Critical dose (8 session or more) delivered or not

Fidelity to the intervention model

FFT-LLC therapist and client outcome measures

Therapeutic alliance

Analysis

We will test the effect of FFT-G on primary and secondary outcomes on an intention-to-treat basis using hierarchical linear mixed modelling, with post-treatment and baseline outcomes, trial arm and trial arm by time interaction term as explanatory variables (included in power calculations). Linear mixed models allow repeated measures from each participant to be correlated by fitting random intercepts varying at the level of the individual, thereby improving precision of estimates. We will analyse differences in treatment outcomes in subgroups (e.g., by gender, age, temperamental irritability, CU traits and presence of offending behaviour at baseline identified by caseworker by using interaction terms). We will calculate effect sizes for primary and secondary outcomes. We will use structural equation modelling to test for mediators of treatment (see measures above). Please see IPPE section below for planned analysis of compliance data.

Longitudinal follow-ups

The effect of treatment will be assessed both 6 months after randomisation (at the end of treatment) and 12 months after randomisation (6 months after treatment ends). We will use the latter timepoint as the main assessment of treatment effects. See above for analytical models.

Implementation and process evaluation

Overview

This section presents information about the implementation and process evaluation (IPE). We would aim to deliver a mixed-methods IPE alongside of the Efficacy Study.

The rest of this section covers:

- Research questions
- Research methods

- Approach to analysis

Research questions

This IPE has been designed in line with YEF guidance on IPEs.

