This is a parallel, two-armed, multi-site, efficacy randomised controlled trial of FFT-G compared to Services as Usual (SAU) interventions, in child social work, youth offending and early intervention services for YP at risk of Child Criminal Exploitation (CCE). This will use block randomisation with randomly varying block sizes of 4 or 6 with equal allocation ratio in order to ensure the research team are blind to the randomisation outcome. We will use small block sizes to ensure full caseloads for the clinical teams. The YP will be the unit of randomisation with an allocation ratio of 1:1, stratified by recruiting site. All study participants will have an allocated caseworker and will receive statutory or other services provided or organized by child social care and other agencies (e.g., early help, Youth Offending Services). In addition, the intervention arm will receive FFT-G and the SAU arm will receive additional specialist services identified prior to randomisation.

Trial design, including number of arms		Two-arm randomised, stratified, parallel group, multi-site efficacy trial
Unit of randomisation		Young person
Stratification variables (if applicable)		Site
Drimon	variable	Offending
Primary outcome	measure (instrument, scale, source)	Measured by YP report: International Self-Report Delinquency Study 4 survey offending scale (ISRD4; Marshall et al., 2022)

_

⁵ See https://youthendowmentfund.org.uk/wp-content/uploads/2023/01/FFT-G.-YEF-Feasibility-and-Pilot.-Jan-2023.pdf.

	variable(s)	YP mental health and adjustment; Child Criminal Exploitation; substance misuse; parental mental health; parental monitoring and supervision; family functioning; parental self-efficacy; attachment representation; YP self-efficacy; Callous-Unemotional (CU) traits; temperamental irritability; school attendance and truancy; age; gender; ethnicity; SES; household composition; service being seen; parent relationship to YP; days from first caseworker contact to randomisation.
	measure(s) (instrument, scale, source)	YP mental health and adjustment measured by Parent and YP report: Strengths and Difficulties Questionnaire (Goodman, 2005)
		Child Criminal Exploitation measured by YP report: SRD4 additional items.
		Substance Misuse measured by YP report: ISRD3 substance misuse subscale (Marshall et al., 2013).
Secondary		Parental mental health measured by parent report: DASS-21 (Henry & Crawford, 2005)

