imputation techniques but the precise techniques used will depend on the pattern and extent of missingness. We will comply with the YEF Guidance on Missing Data.

Compliance

We use FFT LLC's own guidance of defining and measuring family compliance with the intervention. This stipulates that the total dose will depend on the needs of the family. However, we will report on the number of families who attended at least one session, and consider how many families moved through how many phases of treatment, how many received a critical dose of 8 sessions, mean number of sessions received and how many were deemed to have completed treatment. We will also report on therapist fidelity to the FFT model. This data will be provided by FFT LLC using the clinical monitoring system completed by FPM therapists. We will also explore whether time from referral to first FFT session is associated with compliance and improvement in outcomes. If power permits, we will explore whether compliance and fidelity are associated with improvements in the primary outcome and in CCE and SDQ conduct problems.

As advised by the YEF Statistical Guidance we will use an Instrumental Variable approach. This will use a Two Stage Least Square Analysis guidance (2SLS) approach with group allocation as the instrumental variable for the compliance indicator. Results for the first stage will be reported alongside with i) the correlation between the instrument and the endogenous variable; and, ii) a F test.

Intra-cluster correlations (ICCs)

This is not applicable to the current trial.

Presentation of outcomes

Effect sizes will be calculated using Hedges' g. Hedges' g is specified using the following formula:

```
Hedges' g = (x1 - x2) / V((n1-1)*s12 + (n2-1)*s22) / (n1+n2-2) where:
```

x1, x2: The sample 1 mean and sample 2 mean, respectively

n1, n2: The sample 1 size and sample 2 size, respectively

s12, s22: The sample 1 variance and sample 2 variance, respectively

The confidence interval for the Hedge's g statistic is:

g±φ - 1 (1-(α /2))gse where:

 ϕ - 1 = the percent point function of the normal distribution

gse= the standard error of the g statistic

 $= \sqrt{(n1+n2)/n1n2 + g^2/2(n1+n2)}$

References

We will add in to revised version.

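### Allocation to FFT-G also replaces the offer of the SAU specialist service, so the 2SLS complier effect may be biased, in a direction the documents leave open

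*SAP*

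**What the plan says.** The SAP, under Compliance, commits to 2SLS, an "approach with group allocation as the instrumental variable for the compliance indicator". It will report the first-stage correlation and an F test. It does not say which measure is the indicator, which outcomes the 2SLS covers, or what the method assumes, and it plans no sensitivity analysis. The same section lists several candidate measures: at least one session, phases reached, completion, mean sessions, and "how many received a critical dose of 8 sessions". The Protocol's Compliance list has the last of these as a yes/no item: "Critical dose (8 session or more) delivered or not".

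On what each arm is offered, the documents agree. SAP, Design overview: "the intervention arm will receive FFT-G and the SAU arm will receive additional specialist services identified prior to randomisation". Protocol, Design: "the intervention arm will receive FFT-G and the SAU arm will receive additional specialist services identified prior to recruitment". Protocol, Consultation, adds that for an eligible case "an SAU service is identified (if it had not already been by the agency), should the case be randomised to SAU". The control-condition paragraph of the Protocol's Intervention section says the choice is made beforehand "to ensure that an SAU intervention is available directly after randomization". Care common to both arms is also stated: "All study participants will have an allocated caseworker and will receive statutory or other services".

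**The concern.** An instrument must act on the outcome only through the treatment indicator (the exclusion restriction). Here allocation changes two offers: FFT-G, and an active specialist service. The Protocol's examples of that service include mentoring, counselling, parenting programmes and gang-exit work. Take a family that would never engage with FFT-G. Allocated to SAU, it is offered the specialist service; allocated to FFT-G, it is not, as far as the plan is written. If the service matters, the arms differ among non-compliers, and 2SLS attributes that difference to FFT-G in compliers.

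Some non-compliance is foreseeable. The Protocol says participation is voluntary, describes likely participants as possibly resistant to services, and allows for some attrition in its delivery capacity. The two planned diagnostics measure the strength of the instrument and cannot reveal a failure of exclusion. The risk is that one figure is reported as the effect of receiving FFT-G on an assumption that is neither stated nor examined.

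**Working it through.** **Inputs.** The documents state no compliance rate, complier effect or SAU effect, so there is no figure of the plan's own to reproduce. The values of p, d, q and the partial-attendance effects below are assumptions. Effects are benefits in SD units, positive when FFT-G does better. I assume no SAU family receives FFT-G.

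- p: share of FFT-G families who comply.
- C: effect of FFT-G versus the SAU service among compliers.
- δ: average effect of allocation among non-compliers.

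**Identity.**

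ITT = p × C + (1 − p) × δ, and the first stage equals p, so

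2SLS = ITT / p = C + ((1 − p) / p) × δ.

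With any non-compliers, this equals C only if δ = 0. The first-stage correlation and F test depend on p and the sample size, not on δ.

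**Route 1, lost service.** Let d be the benefit of the SAU service over common care in non-compliers, and q the share of FFT-G non-compliers who never receive such a service. Then δ = −q × d. With q = 1, the understatement ((1 − p) / p) × d is:

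| p | d = 0.1 | d = 0.2 | d = 0.3 |
|---|---|---|---|
| 0.9 | 0.011 | 0.022 | 0.033 |
| 0.8 | 0.025 | 0.050 | 0.075 |
| 0.7 | 0.043 | 0.086 | 0.129 |
| 0.6 | 0.067 | 0.133 | 0.200 |
| 0.5 | 0.100 | 0.200 | 0.300 |

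With q = 0.5 each entry halves; with q = 0 or d = 0 it is zero.

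For illustration set C = 0.36, the pilot effect used for the sample size, and d = 0.2, q = 1:

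- p = 0.9: 0.36 − 0.022 = 0.34 (6% low).
- p = 0.7: 0.36 − 0.086 = 0.27 (24% low).
- p = 0.5: 0.36 − 0.200 = 0.16 (56% low).

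A simulation with 2,000,000 families per scenario agrees: at p = 0.7, d = 0.2 it gives 0.273 for q = 1 (formula 0.274) and 0.360 for q = 0.

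**Route 2, partial attendance.** If the indicator is eight or more sessions, non-compliers may have had up to seven. Suppose p = 0.7 and 20% of FFT-G families attend in part, doing better by e than they would have done in SAU. The estimate rises by 0.2 × e / 0.7:

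- e = 0.1: 0.36 + 0.029 = 0.389.
- e = 0.2: 0.36 + 0.057 = 0.417.

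**Net.** Both routes act through δ with opposite signs. The documents do not fix the sign of their sum.

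**Check of the correction.** At p = 0.7, C = 0.36, δ = −0.2: ITT = 0.252 − 0.060 = 0.192. Then (ITT − (1 − p) × δ) / p = (0.192 + 0.060) / 0.7 = 0.36, as it should.

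**The case against.** A reader might infer that FFT-G families who drop out get neither service and that the complier effect is therefore biased low. The documents do not support that. Nothing bars a later referral. Every family keeps a caseworker and statutory or other services. The Protocol describes the SAU options as existing local authority services, and its Consultation section allows that the agency may already have identified one. What non-compliers actually receive is not stated.

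The size can also be contested. If the indicator is attending at least one session, non-compliers may be few, because willingness to engage in family therapy is an entry criterion; at p = 0.9 the shift is 0.01 to 0.03 SD. A stricter indicator could lower p, but then some non-compliers have had FFT-G sessions and the second route applies. The value 0.36 comes from caregiver-reported family functioning, with an interval of −0.32 to 1.03, and not from delinquency. With 288 × 0.9 × 0.9 ≈ 233 followed up and p = 0.7, the 2SLS standard error is about (2 / √233) / 0.7 = 0.19, or 0.16 after adjusting for a baseline correlation of 0.523. A shift of 0.086 is about half of that.

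For compliers, FFT-G against the SAU service is the intended contrast, so replacing one offer with the other is no fault in itself. The SAP cites the funder's statistical guidance for the method. It does not tie the 2SLS to named outcomes, so reading it as the adjusted result for delinquency, criminal exploitation and conduct problems is an inference from the preceding sentence.

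All of this stands, and it limits the point to a possible bias of unknown sign. It does not supply a reason for δ to be zero, and the SAP offers none.

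**Conclusion.** The exclusion restriction is not secured for FFT-G non-compliers, and the SAP neither states nor examines it. The complier effect may be biased. Through the lost-service route alone the shift is 0.01 to 0.30 SD for assumed p of 0.5 to 0.9 and d of 0.1 to 0.3 SD, taking q = 1; later referral reduces it in proportion. If the SAU service were harmful, this shift would reverse. Partial attendance under an eight-session indicator pushes upwards, so the net direction is open. The problem is confined to a supplementary analysis: the primary intention-to-treat comparison does not depend on it.

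**What to change.** In the SAP's Compliance section:

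1. Name one binary compliance indicator for the 2SLS and list the outcomes it applies to. This comes first, because p and δ have no meaning without it.
2. State that the contrast is FFT-G versus the SAU service among compliers, and that 2SLS assumes allocation has no effect in non-compliers.
3. Using the agency activity data planned in Protocol Table 4, tabulate by arm and compliance status who received the specialist service named at consultation. Table 4 lists both arms as sources; confirm that SAU activity will be extracted for FFT-G families too.
4. Beside the 2SLS estimate, report (ITT − (1 − p) × δ) / p over a range of δ fixed before unblinding. A range of −0.3 to +0.3 SD is an illustrative choice; at p = 0.7 it moves the estimate by 0.3 × 0.3 / 0.7 = 0.129 SD either way. Do not present the δ = 0 figure alone.

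The cost is a few lines of text, one tabulation and one short calculation, with no new participants or visits. The downside is that the compliance result becomes a range instead of a single number.
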